13.3. Subject Information and Informed Consent

The Investigator must obtain informed consent of a subject and/or a subject's legal representative prior to any study related procedures.

Documentation that informed consent occurred prior to the study subject's entry into the study and of the informed consent process should be recorded in the study subject's source documents including the date. The original ICF signed and dated by the study subject and by the person consenting the study subject prior to the study subject's entry into the study, must be maintained in the Investigator's study files and a copy given to the study subject. In addition, if a protocol is amended and it impacts on the content of the informed consent, the ICF must be revised. Study subjects participating in the study when the amended protocol is implemented must be reconsented with the revised version of the ICF. The revised ICF signed and dated by the study subject and by the person consenting the study subject must be maintained in the Investigator's study files and a copy given to the study subject.

13.4. Confidentiality

Celgene affirms the subject's right to protection against invasion of privacy and to be in compliance with ICH and other local regulations (whichever is most stringent). Celgene requires the Investigator to permit Celgene's representatives and, when necessary, representatives from regulatory authorities, to review and/or copy any medical records relevant to the study in accordance with local laws

Should direct access to medical records require a waiver or authorization separate from the subject's signed ICF, it is the responsibility of the Investigator to obtain such permission in writing from the appropriate individual.

13.5. Protocol Amendments

Any amendment to this protocol must be approved by the Celgene Clinical Research Physician/Medical Monitor. Amendments will be submitted to the IRB/EC for written approval. Written approval must be obtained before implementation of the amended version occurs. The written signed approval from the IRB/EC should specifically reference the Investigator name, protocol number, study title and amendment number(s) that is applicable. Amendments that are administrative in nature do not require IRB/IEC approval but will be submitted to the IRB/IEC for information purposes.

Any substantial amendment to the protocol will be submitted to Competent Regulatory Authority in each country and will not be implemented until it has been approved.

13.6. Institutional Review Board/Independent Ethics Committee Review and Approval

Before the start of the study, the study protocol, ICF, and any other appropriate documents will be submitted to the IRB/EC with a cover letter or a form listing the documents submitted, their dates of issue, and the site (or region or area of jurisdiction, as applicable) for which approval is sought. If applicable, the documents will also be submitted to the authorities in accordance with local legal requirements.

Investigational product can only be supplied to an Investigator by Celgene or its authorized representative after documentation on all ethical and legal requirements for starting the study has been received by Celgene or its authorized representative. This documentation must also include a list of the members of the IRB/EC and their occupation and qualifications. If the IRB/EC will not disclose the names, occupations and qualifications of the committee members, it should be asked to issue a statement confirming that the composition of the committee is in accordance with GCP. For example, the IRB General Assurance Number may be accepted as a substitute for this list. Formal approval by the IRB/EC should mention the protocol title, number, amendment number (if applicable), study site (or region or area of jurisdiction, as applicable), and any other documents reviewed. It must mention the date on which the decision was made and must be officially signed by a committee member. Before the first subject is enrolled in the study, all ethical and legal requirements must be met.

The IRB/EC and, if applicable, the authorities, must be informed of all subsequent protocol amendments in accordance with local legal requirements. Amendments must be evaluated to determine whether formal approval must be sought and whether the ICF should also be revised.

The Investigator must keep a record of all communication with the IRB/EC and, if applicable, between a Coordinating Investigator and the IRB/EC. This statement also applies to any communication between the Investigator (or Coordinating Investigator, if applicable) and regulatory authorities.

Any advertisements used to recruit subjects for the study must be reviewed by Celgene and the IRB/EC prior to use.

13.7. Ongoing Information for Institutional Review Board/Ethics Committee

If required by legislation or the IRB/EC, the Investigator must submit to the IRB/EC:

- Information on serious or unexpected adverse events as soon as possible;
- Periodic reports on the progress of the study;
- Deviations from the protocol or anything that may involve added risk to subjects.

13.8. Termination of the Study

Celgene reserves the right to terminate this study prematurely at any time for reasonable medical or administrative reasons. Any premature discontinuation will be appropriately documented according to local requirements (eg, IRB/EC, regulatory authorities, etc).

In addition, the Investigator or Celgene has the right to discontinue a single site at any time during the study for medical or administrative reasons such as:

- Unsatisfactory enrollment;
- GCP noncompliance;
- Inaccurate or incomplete data collection;
- Falsification of records:
- Failure to adhere to the study protocol.

14. DATA HANDLING AND RECORDKEEPING

14.1. Data/Documents

The Investigator must ensure that the records and documents pertaining to the conduct of the study and the distribution of the investigational product are complete, accurate, filed and retained. Examples of source documents include: hospital records; clinic and office charts; laboratory notes; memoranda; subject's diaries or evaluation checklists; dispensing records; recorded data from automated instruments; copies or transcriptions certified after verification as being accurate copies; microfiche; x-ray film and reports; and records kept at the pharmacy, and the laboratories, as well as copies of CRFs or CD-ROM.

14.2. Data Management

Data will be collected via CRF and entered into the clinical database per Celgene standard operating procedures (SOPs). This data will be electronically verified through use of programmed edit checks specified by the clinical team. Discrepancies in the data will be brought to the attention of the clinical team, and investigational site personnel, if necessary. Resolutions to these issues will be reflected in the database. An audit trail within the system will track all changes made to the data.

14.3. Record Retention

Essential documents must be retained by the Investigator according to the period of time outlined in the clinical trial agreement. The Investigator must retain these documents for the time period described above or according to local laws or requirements, whichever is longer. Essential documents include, but are not limited to, the following:

- Signed ICFs for all subjects;
- Subject identification code list, screening log (if applicable), and enrollment log;
- Record of all communications between the Investigator and the IRB/EC;
- Composition of the IRB/EC;
- Record of all communications between the Investigator, Celgene, and their authorized representative(s);
- List of subinvestigators and other appropriately qualified persons to whom the Investigator has delegated significant study-related duties, together with their roles in the study, curriculum vitae, and their signatures;
- Copies of CRFs (if paper) and of documentation of corrections for all subjects;
- IP accountability records;
- Record of any body fluids or tissue samples retained;
- All other source documents (subject records, hospital records, laboratory records, etc.);

• All other documents as listed in Section 8 of the ICH consolidated guideline on GCP (Essential Documents for the Conduct of a Clinical Trial).

The Investigator must notify Celgene if he/she wishes to assign the essential documents to someone else, remove them to another location or is unable to retain them for a specified period. The Investigator must obtain approval in writing from Celgene prior to destruction of any records. If the Investigator is unable to meet this obligation, the Investigator must ask Celgene for permission to make alternative arrangements. Details of these arrangements should be documented.

All study documents should be made available if required by relevant health authorities. Investigator or institution should take measures to prevent accidental or premature destruction of these documents.

15. QUALITY CONTROL AND QUALITY ASSURANCE

All aspects of the study will be carefully monitored by Celgene or its authorized representative for compliance with applicable government regulations with respect to current GCP and SOPs.

15.1. Study Monitoring and Source Data Verification

Celgene ensures that appropriate monitoring procedures are performed before, during and after the study. All aspects of the study are reviewed with the Investigator and the staff at a study initiation visit and/or at an Investigators' Meeting. Prior to enrolling subjects into the study, a Celgene representative will review the protocol, CRFs, procedures for obtaining informed consent, record keeping, and reporting of AEs/SAEs with the Investigator. Monitoring will include on-site visits with the Investigator and his/her staff as well as any appropriate communications by mail, email, fax, or telephone. During monitoring visits, the facilities, investigational product storage area, CRFs, subject's source documents, and all other study documentation will be inspected/reviewed by the Celgene representative in accordance with the Study Monitoring Plan.

Accuracy will be checked by performing source data verification that is a direct comparison of the entries made onto the CRFs against the appropriate source documentation. Any resulting discrepancies will be reviewed with the Investigator and/or his/her staff. Any necessary corrections will be made directly to the CRFs or via queries by the Investigator and/or his/her staff. Monitoring procedures require that informed consents, adherence to inclusion/exclusion criteria and documentation of SAEs and their proper recording be verified. Additional monitoring activities may be outlined in a study-specific monitoring plan.

15.2. Audits and Inspections

In addition to the routine monitoring procedures, a Good Clinical Practice Quality Assurance unit exists within Celgene. Representatives of this unit will conduct audits of clinical research activities in accordance with Celgene SOPs to evaluate compliance with Good Clinical Practice guidelines and regulations.

The Investigator is required to permit direct access to the facilities where the study took place, source documents, CRFs and applicable supporting records of study subject participation for audits and inspections by IRB/ECs, regulatory authorities (eg, Food and Drug Administration [FDA], European Medicines Agency [EMA], Health Canada) and company authorized representatives. The Investigator should make every effort to be available for the audits and/or inspections. If the Investigator is contacted by any regulatory authority regarding an inspection, he/she should contact Celgene immediately.

16. PUBLICATIONS

As described in Section 13.2, all protocol- and amendment-related information, with the exception of the information provided by Celgene on public registry websites, is considered Celgene confidential information and is not to be used in any publications. Celgene protocol-related information proposed for use in a publication must be submitted to Celgene for review and approval, and should not be utilized in a publication without express written approval from Celgene, or as described in the Clinical Trial Agreement.

Celgene will ensure Celgene-sponsored studies are considered for publication in the scientific literature in a peer-reviewed journal, irrespective of the results. At a minimum, this applies to results from all Phase 3 clinical studies, and any other study results of significant medical importance. This also includes results relating to investigational medicines whose development programs have been discontinued.

Study results may also be presented at one or more medical congresses, and may be used for scientific exchange and teaching purposes. Additionally, this study and its results may be submitted for inclusion in all appropriate health authority study registries, as well as publication on health authority study registry websites, as required by local health authority regulations.

Eligibility for external authorship, as well as selection of first authorship, will be based on several considerations, including, but not limited to, contribution to protocol development, study recruitment, data quality, participation in data analysis, participation in study steering committee (when applicable) and contribution to abstract, presentation and/or publication development.

18. APPENDICES

Appendix A: Table of Abbreviations

Appendix A: Table of Appreviations Abbreviation or		
Specialist Term	Explanation	
AE	Adverse event	
AESI	Adverse event of special interest	
ALP	Alkaline phosphatase	
ALT	Alanine aminotransferase	
ANC	Absolute neutrophil count	
ASCT	autologous stem cell transplantation	
AST	Aspartate aminotransferase	
AUC	Area under the curve	
β-hCG	β-subunit of human chorionic gonadotropin	
BM	Bone marrow	
BMA	Bone marrow aspirate	
BMB	Bone marrow biopsy	
BUN	Blood urea nitrogen	
CBC	Complete blood count	
CD	Cluster of differentiation	
C _{max}	Maximum plasma concentration of drug	
CNS	Central nervous system	
COPD	chronic obstructive pulmonary disease	
CR	Complete response	
CrCl	Creatinine clearance	
CRF	Case report form	
CT	Computed tomography	
CTCAE	Common Terminology Criteria for Adverse Events	
CTLA-4	Cytotoxic T-lymphocyte-associated antigen 4	
D^2	Durvalumab + daratumumab	
DARA	Daratumumab	
dex	Dexamethasone	
DLT	Dose-limiting toxicity	

Abbreviation or Specialist Term	Explanation	
DRT	Dose Review Team	
DURVA	Durvalumab	
EC	Ethics Committee	
eCRF	electronic case report form	
ECG	Electrocardiogram	
ECOG	Eastern Cooperative Oncology Group	
EE	Efficacy Evaluable (population)	
EEA	European Economic Area	
EMA	European Medicines Agency	
EMP	Extramedullary plasmacytoma	
EOI	End of infusion	
EOT	End of Treatment	
EU	European Union	
Fc	Fragment crystallizable	
FCBP	Female of child-bearing potential	
FDA	Food and Drug Administration	
GCP	Good Clinical Practice	
GLP	Good Laboratory Practice	
HIV	Human immunodeficiency virus	
IAT	Indirect Antiglobulin Test	
IB	Investigator's Brochure	
ICF	Informed consent form	
ICH	International Council for Harmonisation	
IgA	immunoglobulin A	
IgD	immunoglobulin D	
IgE	immunoglobulin E	
IgG	immunoglobulin G	
IgM	immunoglobulin M	
IMiDs [®]	immunomodulatory drugs	
IMWG	International Myeloma Working Group	
IND	Investigational New Drug	

Abbreviation or Specialist Term	Explanation	
IP	Investigational Product	
IRB	Institutional Review Board	
IRT	Interactive Response Technology	
ILD	Interstitial lung disease	
imAE	Immune-mediated adverse event	
IV	Intravenous	
LEN	lenalidomide	
mAb	Monoclonal antibody	
MedDRA	Medical Dictionary for Regulatory Activities	
MM	Multiple myeloma	
MR	Minimal response	
MRI	Magnetic resonance imaging	
NCCN	National Comprehensive Cancer Network	
NCI	National Cancer Institute	
NK	Natural Killer	
NOAEL	No observed adverse effect level	
ORR	Overall response rate	
PCP	Pneumocystis carinii pneumonia	
PD	Progressive disease	
PD-1	Programmed cell ceath-1	
pDCs	Plasmacytoid dendritic cells	
PD-L1	Programmed cell death ligand 1	
PD-L2	Programmed cell death ligand 2	
PFS	Progression-free survival	
PI	Prescribing Information; proteasome inhibitor	
PK	Pharmacokinetics	
POM	Pomalidomide	

Abbreviation or Specialist Term	Explanation	
PR	Partial response	
Q4W	Every four weeks	
RBC	Red blood cell count	
RP2D	recommended phase 2 doses	
RRMM	Relapsed and refractory multiple myeloma	
SAE	Serious adverse event	
SAP	Statistical Analysis Plan	
SD	Stable Disease	
SmPC	Summary of product characteristics	
SOP	Standard operating procedure	
sPEP	Serum protein electrophoresis	
SPM	Second primary malignancy	
SUSAR	Suspected unexpected serious adverse reaction	
t _{1/2}	Terminal elimination half-life	
TNF	Tumor necrosis factor	
Tregs	regulatory T cells	
TSH	Thyroid stimulating hormone	
ULN	Upper limit of normal	
uPEP	Urine protein electrophoresis	
US/USA	United States/United States of America	
VGPR	Very Good Partial Response	
VTE	Venous thromboembolism	

Appendix B: International Myeloma Working Group Uniform Response Criteria

Response Category ^a	Response Criteria	
Stringent Complete Response (sCR)	CR as defined below, plus Normal serum free light chain (FLC) ratio and Absence of clonal plasma cells by immunohistochemistry or 2- to 4-color flow cytometry	
Complete Response (CR)	Negative immunofixation of serum and urine and Disappearance of any soft tissue plasmacytomas and ≤ 5% plasma cells in bone marrow In patients in whom the only measurable disease is by serum FLC levels: CR in such patients indicates a normal FLC ratio of 0.26 to 1.65 in addition to CR criteria listed above.	
Very Good Partial Response (VGPR)	Serum and urine M-protein detectable by immunofixation but not on electrophoresis or 90% or greater reduction in serum M-protein plus urine M-protein level <100 mg per 24 hours In patients in whom the only measurable disease is by serum FLC levels: VGPR in such patients requires a > 90% decrease in the difference between involved and uninvolved FLC levels.	
Partial Response (PR)	\geq 50% reduction of serum M-Protein and reduction in 24-hour urinary M-protein by \geq 90% or to < 200 mg per 24 hours If the serum and urine M-protein are not measurable, a \geq 50% decrease in the difference between involved and uninvolved FLC levels is required in place of the M-protein criteria. If serum and urine M-protein are unmeasurable, and the serum free light chain assay is also unmeasurable, a \geq 50% reduction in plasma cells is required in place of M-protein, provided baseline bone marrow plasma cell percentage was \geq 30% In addition to the above, if present at baseline a \geq 50% reduction in the size of soft tissue plasmacytomas is also required.	
Stable Disease (SD)	Not meeting criteria for CR, VGPR, PR, or PD	

Response Category ^a	Response Criteria	
Progressive disease (PD)	Requires only one of the following:	
	Increase of 25% from lowest response value in any of the following:	
	 Serum M-component (absolute increase must be ≥ 0.5 g/dL), and/or 	
	 Urine M-component (absolute increase must be ≥ 200 mg/24 h), and/or 	
	Only in patients without measurable serum and urine M-protein levels: the difference between involved and uninvolved FLC levels (absolute increase must be ≥ 10 mg/dL)	
	Only in patients without measurable serum and urine M protein levels and without measurable disease by FLC levels, bone marrow plasma cell percentage (absolute percentage must be $\geq 10\%$)	
	Definite development of new bone lesions or soft tissue plasmacytomas or definite increase in the size of existing bone lesions or soft tissue plasmacytomas	
	Development of hypercalcemia (corrected serum calcium > 11.5 mg/dL) that can be attributed solely to the plasma cell proliferative disorder	
Additional Response Crite	eria	
Molecular Complete Response	CR plus negative allele-specific oligonucleotide polymerase chain reaction (ASO-PCR), sensitivity 10 ⁻⁵	
Immunophenotypic	Stringent CR plus	
Complete Response	Absence of phenotypically aberrant plasma cells (clonal) in BM with a minimum of 1 million total BM cells analyzed by multiparametric flow cytometry (with > 4 colors)	
Minimal Response (MR)	≥ 25% but ≤ 49% reduction of serum M-protein and reduction in 24-hour urine M-protein by 50%-89%	
in patients with relapsed refractory myeloma adopted from the European Group for Blood and	In addition to the above criteria, if present at baseline, 25%-49% reduction in the size of soft tissue plasmacytomas is also required	
Marrow Transplantation (EBMT) criteria	No increase in size or number of lytic bone lesions (development of compression fracture does not exclude response)	

a All response categories (CR, sCR, VGPR, PR, and PD) require 2 consecutive assessments made at any time before the institution of any new therapy; CR, sCR, VGPR, PR, and SD categories also require no known evidence of progressive or new bone lesions if radiographic studies were performed. VGPR and CR categories require serum and urine studies regardless of whether disease at baseline was measurable on serum, urine, both, or neither. Radiographic studies are not required to satisfy these response requirements. Bone marrow assessments need not be confirmed. For PD, serum M-component increases of more than or equal to 1 g/dL are sufficient to define relapse if the starting M-component is ≥ 5 g/dL.

Source: Rajkumar, 2011

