2. STUDY OBJECTIVES AND ENDPOINTS

Table 1: Study Objectives

Primary Objective

The primary objective of the study is to determine the safety and efficacy of D^2 in subjects with RRMM.

Secondary Objectives

The secondary objectives are:

- Evaluate additional measures of efficacy of D² in subjects with RRMM
- Evaluate the pharmacokinetics (PK) of DURVA and DARA in subjects with RRMM

[figure not shown]

Table 2: Study Endpoints

Endpoint	Name	Description
Primary	Overall response rate (ORR)	Tumor response, including progressive disease (PD) according to the International Myeloma Working Group (IMWG) Uniform Response Criteria (Rajkumar, 2011).
Primary	Safety	Type, frequency, seriousness and severity of adverse events (AEs), and relationship of AEs to study treatment
Secondary	Time-to-response (TTR)	Time from enrollment to the first documentation of response (Partial Response [PR] or greater)
Secondary	Duration of response (DOR)	Time from the first documentation of response (PR or greater) to the first documentation of PD

Table 2: Study Endpoints (Continued)

Endpoint	Name	Description
Secondary	Progression-free survival (PFS)	Time from enrollment to the first documentation of PD or death from any cause during study, whichever occurs earlier
Secondary	PK parameters	Typical serum/plasma PK parameters for DURVA and DARA, such as maximum observed concentration (C_{max}) area under the concentration-time curve (AUC), time to maximum concentration (T_{max}), terminal elimination half-life ($t_{1/2}$), clearance (CL/F), and volume of distribution (V_z /F)

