- b On Cycle 1 Day 1 (C1D1), safety laboratory assessments must be performed locally to confirm subject continues to meet the required safety laboratory values prior to initiating study treatment. However, if screening assessments were performed within 72 hours of C1D1, safety laboratory and physical examinations need not be repeated at C1D1.
- c Per IMWG Uniform Response Criteria all response categories and progressive disease require 2 consecutive assessments.
- d Preinfusion medications to be given before all daratumumab infusions (if necessary, oral preinfusion medications may be administered at the subject's home on the day of the infusion, provided they are given within 3 hours prior to the infusion); postinfusion medications to be given on the first and second days following all daratumumab infusions.
- e Every effort should be made to keep subjects on the planned dosing schedule. However, doses given within 3 days of the scheduled dose are permitted, as long as the interval between doses is at least 5 days. Blood pressure is to be measured at the following time points on C1D1 and C1D8: immediately before the start of the infusion; at 30 minutes, 1 hour, 90 minutes, 2 hours, and 3 hours 30 minutes after the start of the infusion; at the end of the infusion; and 30 minutes and 1 hour after the end of the infusion. For all other DARA infusions, blood pressure will be measured immediately before the infusion start and at the end of the infusion.
- f First DURVA infusion: blood pressure and pulse will be monitored, as follows (based on a 60-minute infusion): Prior to the beginning of the infusion (measured once from approximately 30 minutes before up to 0 minutes [i.e., the beginning of the infusion]); approximately 30 minutes during the infusion (halfway through infusion); at the end of the infusion (approximately 60 minutes ±5 minutes). If the infusion takes longer than 60 minutes, then BP and pulse measurements should follow the principles as described above or be taken more frequently if clinically indicated. For DURVA infusions on C2D1 onward, a +24 hours window is allowed and may be implement per investigator discretion.

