6.4.5. Assessment of Response

Starting from Cycle 2, response will be assessed by the investigators using the International Myeloma Working Group (IMWG) Uniform Response Criteria (Rajkumar, 2011) (Appendix B) at every cycle on Day 1 and at the EOT Visit. Response must be based on the central laboratory data to ensure consistency across investigative sites.

NOTE: Per IMWG Uniform Response Criteria all response categories and progressive disease require 2 consecutive assessments except for radiographic or bone marrow assessments

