9.2. Study Population Definitions

The following 5 populations will be used for analysis:

- Safety Population: all enrolled subjects who take at least 1 dose of any study treatment. All safety analyses will be based on this population
- Dose-limiting Toxicity Evaluable Population: all subjects from the Safety Population who meet the minimum exposure criterion and have sufficient safety evaluations, or experience a DLT during the first treatment cycle.
- Full Analysis Population: all subjects who are enrolled in this study.
- Efficacy Evaluable (EE) Population: all enrolled subjects who take at least 1 dose of study treatment and who have measurable disease at baseline and at least one postbaseline efficacy assessment.
- Pharmacokinetic Population: includes all subjects who receive at least 1 dose of study treatment and have at least 1 measureable plasma exposure. If any subjects are found to be noncompliant with respect to dosing, have incomplete data, or encounter other circumstances that would affect the evaluation of the PK, a decision will be made on a case-by-case basis as to the inclusion of his PK data in the statistical analysis.

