9.8.4. Progression-free survival (PFS)

Progression-free survival will be calculated as the time between the enrollment and PD, as determined by the investigator using the IMWG criteria, or death, whichever occurred earlier. Subjects who do not have a PFS event will be censored on the last adequate response assessment date. Progression-free survival will be summarized for full analysis population using Kaplan-Meier statistics as appropriate or listed by dose cohort and arm.

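### Laboratory PD first seen at the last assessment is tabulated as SD on a literal reading, and the plan does not settle whether it is a PFS event

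*Combined protocol and SAP*

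**What the plan says.** **Confirmation.** The footnote to Appendix B states: "All response categories (CR, sCR, VGPR, PR, and PD) require 2 consecutive assessments made at any time before the institution of any new therapy". Section 6.4.5 repeats the rule with an exception: "all response categories and progressive disease require 2 consecutive assessments except for radiographic or bone marrow assessments". Footnote c of Table 4 gives it without the exception: "Per IMWG Uniform Response Criteria all response categories and progressive disease require 2 consecutive assessments".

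**SD.** Appendix B defines SD as "Not meeting criteria for CR, VGPR, PR, or PD". SD is not among the categories that need two assessments. One limit applies: "CR, sCR, VGPR, PR, and SD categories also require no known evidence of progressive or new bone lesions if radiographic studies were performed".

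**Response table.** Entry to the EE population (Section 9.2) needs only "at least one postbaseline efficacy assessment". Section 9.8.1 tabulates CR, VGPR, PR, SD and PD, with no row for unconfirmed PD. The primary response endpoint in Table 2 is described as "Tumor response, including progressive disease (PD) according to the International Myeloma Working Group (IMWG) Uniform Response Criteria".

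**PFS.** Table 2 takes PD when first documented, or death on study. Section 9.8.4 takes investigator-determined PD under the IMWG criteria, or death, and adds: "Subjects who do not have a PFS event will be censored on the last adequate response assessment date". What makes an assessment adequate is not defined.

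**DOR.** Table 2 ends DOR at the first documented PD. Section 9.8.3 ends it on the date progression was confirmed, and gives no censoring rule.

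**Schedule.** Response is assessed on Day 1 of each cycle from Cycle 2 and at EOT (Section 6.4.5). Table 4 has no electrophoresis, immunofixation, free light chain or response assessment at the 28-day or 90-day follow-up visits.

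**The concern.** PD has to be seen twice, SD does not have to be seen at all, and the schedule can end on the visit where PD first appears. A progression that was observed then has no place in the response table except SD. This is different from a subject who stops without evidence of progression: here the evidence exists and the classification rule sets it aside.

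Two results are at stake. The primary response endpoint expressly includes PD, so the PD proportion may be understated and SD overstated. If the same visit also becomes a PFS censoring date, the censoring is triggered by apparent progression. That is informative, and it biases the Kaplan-Meier curve upward.

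**Working it through.** The documents give no figure for PFS or for unconfirmed PD, so there is no plan figure to reproduce. The check is a trace of the rules, then an illustration of size.

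**Step 1: trace of the rules**

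| Situation | Section 9.8.1 category if no earlier response | PFS |
|---|---|---|
| Laboratory PD on Day 1, repeated at the next Day 1 or at EOT, no new therapy between | PD | Event |
| M-protein or free light chain PD first seen at EOT | SD | Censored at that visit if PD must be confirmed (and the visit is adequate); event if Table 2 is followed |
| One laboratory PD value, then new therapy or withdrawal before a second | SD | Same two readings |
| One laboratory PD value, then death on study | SD | Event, at death at the latest |
| PD on imaging or bone marrow | PD (exempt under Section 6.4.5) | Event |

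Calcium is a partial exception. The chemistry panel continues at the follow-up visits (Section 6.3.1), so a second calcium value may exist, but no response assessment is scheduled there to use it.

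**Step 2: ORR and the Simon rule.** ORR is the count of subjects with PR or better, divided by the EE count. Moving k subjects from PD to SD changes neither number. The rules (stop at 11 or fewer of 32; reject at 39 or more of 100) use only the count of responders, so they do not change.

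**Step 3: response table.** Each affected subject moves 1/N from PD to SD. With the planned 32 subjects of Stage 1 that is 1/32 = 3.1 percentage points per subject.

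**Step 4: PFS, on the reading that PD must be confirmed.** Let u be the share of all PFS events, deaths included, that is recoded as censored on the event date, at random over time. The estimated hazard becomes (1-u) times the true one, so S*(t) = S(t)^(1-u). With exponential PFS the median is multiplied by 1/(1-u).

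| u (assumed) | Multiplier of the median |
|---|---|
| 5% | 1/0.95 = 1.05 |
| 10% | 1/0.90 = 1.11 |
| 20% | 1/0.80 = 1.25 |
| 30% | 1/0.70 = 1.43 |

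A version on the visit grid, assuming a true median of 4 months, 28-day visits and 30.4 days per month:

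- Six cycles = 168/30.4 = 5.53 months, so true PFS = 0.5^(5.53/4) = 38.4%.
- Hazard per cycle h = 1 - 0.384^(1/6) = 0.1475.
- With recoding, PFS at six cycles = (1 - (1-u)h)^6. This gives 42.5% at u = 10%, 47.1% at 20% and 52.0% at 30%.
- A simulation of 400,000 subjects gave 38.3%, 42.5%, 47.0% and 52.0% for u = 0, 10%, 20% and 30%.

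**Step 5: from progressors to events.** If f is the share of progressions never confirmed and d the share of PFS events that are deaths, then u is at most f(1-d). For an assumed d = 20%, f = 10% gives u = 8% and a multiplier of 1/0.92 = 1.09; f = 30% gives u = 24% and 1/0.76 = 1.32.

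**The case against.** The strongest reply is that the documents are silent on a single unconfirmed PD, and that silence is not a rule. Table 2 and Section 9.8.4 do not say confirmed; only Section 9.8.3 does, and only for DOR. An analyst could count one documented PD as a PFS event and be within the text. This stands. A reader might infer that such subjects are definitely censored for PFS on the day of progression. The documents do not support that, because the two definitions point in different directions and adequate is undefined. They do leave two analysts free to code the same subject differently.

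A reader might also infer that any PD at the last assessment is lost. That is too broad. Imaging and marrow findings are exempt, SD is barred when radiographs show progressive or new bone lesions, and a death on study is an event.

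The route is also narrow. A subject with one raised value who stays on treatment has another assessment at the next Day 1, and the EOT draw will confirm many Day 1 progressions. Efficacy laboratories are central, so stopping on the day of the first PD value is unlikely. What remains is mainly PD first seen at EOT, early new therapy, and withdrawal. On new therapy, Section 3.1.1.3 ties the addition of POM + dex to confirmed PD, while Section 3.2 says only PD; these passages must be reconciled.

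For DOR, a reader might infer censoring at progression. Section 9.8.3 has no DOR censoring rule, so the supported point is only that its end date conflicts with Table 2.

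Finally, some single PD values are laboratory noise, so treating all of them as true progression would be wrong in the other direction. That is a reason to report both versions.

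**Conclusion.** The point holds for laboratory PD. Read literally, Appendix B and Section 9.8.1 place a first laboratory PD at the only or last assessment under SD when there is no earlier response. For PFS the passages conflict, and censoring at that visit is one of two open readings. The PD rate may therefore be understated, and SD and PFS overstated.

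The size is unknown because the documents do not give the share affected. The multipliers 1.05 (u = 5%) and 1.11 (u = 10%) assume exponential PFS and recoding at random over time. The larger multipliers show the range and are not forecasts, since the EOT draw and deaths on study both reduce u.

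ORR and the Simon decision do not change. What moves is the split between SD and PD among non-responders and a descriptive secondary endpoint. Enrollment has been discontinued, so 32 is a planned number; in a smaller cohort each recoded subject weighs more.

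**What to change.** 1. In Section 9.8.1, report laboratory PD at the last assessment without a confirming assessment in its own row, 'PD, unconfirmed', when the subject has no earlier confirmed response or SD. Do not count it as SD. Keep the subject in the EE denominator as a non-responder.
2. In Section 9.8.4, reconcile Table 2 with Appendix B by stating which PD definition is primary and what counts as an adequate assessment. Report PFS both ways: confirmed PD only, and with unconfirmed PD at the last assessment counted as an event on that date.
3. Reconcile the end of DOR between Table 2 and Section 9.8.3, and footnote c of Table 4 with the exception in Section 6.4.5.

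The cost is a few sentences, one table row and one extra PFS run, with no new visits or data. The downside is that some single PD values may be laboratory noise, so the second PFS analysis may read slightly short.
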